Appendix 3 ***Schedule of Activities for the PPMS Cohort (cont.)***

- ^q Local blood flow cytometry and blood TBNK/B-cell subset panel samples (where indicated at the same timepoints as CSF, including optional relapse CSF) should be collected on the same day and as close as possible in time to the CSF sample, even if CSF is collected prior to ocrelizumab administration by up to 7 days.
- ^r Neurological examinations will be used to distinguish relapse in MS from another neurological (non-MS) disorder. Potential relapses should be recorded throughout the treatment period. Investigators will also screen patients for signs and symptoms of PML by evaluating neurological deficits localized to the cerebral cortex, such as cortical symptoms/signs, behavioral and neuropsychological alteration, retrochiasmal visual defects, hemiparesis, cerebellar symptoms/signs (e.g., gait abnormalities, limb incoordination). Patients with suspected PML should be withheld from ocrelizumab treatment until PML is ruled out by complete clinical evaluation and appropriate diagnostic testing (see [Appendix 6](#)). A patient with confirmed PML should be withdrawn from the study. PML should be reported as a serious adverse event (with all available information) with immediate notification of the Medical Monitor.
- ^s If an MRI was obtained during the 4-week screening period then that MRI can be used as the baseline brain MRI and the brain MRI does not need to be repeated at baseline (Day 1).
- ^t Adverse events will be reported throughout the study and for up to 48 weeks after the last dose of ocrelizumab as provided through this study. If the patient is unable to return for the safety follow-up visit, the discontinuation visit information may be captured via phone call.
- ^u Medications used after treatment discontinuation should be recorded during the Safety Follow-up Period.
- ^v All patients must receive prophylactic treatment with 100 mg methylprednisolone (or equivalent), administered by slow IV infusion, to be completed approximately 30 minutes before the start of each ocrelizumab infusion.
- ^w Ocrelizumab 600 mg will be administered as two 300-mg IV infusions separated by 14 days at a scheduled interval of every 24 weeks.
- ^x For patients consenting to optional RCR sampling only. Not applicable in countries not participating in RCR sampling.
- ^y For DNA collection, only a single sample is needed and will be obtained at baseline. However, if the sample collection is missed for any reason, the sample may be obtained at any subsequent visit.

Appendix 4

Expanded Disability Status Scale

Kurtzke Expanded Disability Status Scale (EDSS)

- 0.0 - Normal neurological exam (all grade 0 in all Functional System (FS) scores*).
- 1.0 - No disability, minimal signs in one FS* (i.e., grade 1).
- 1.5 - No disability, minimal signs in more than one FS* (more than 1 FS grade 1).
- 2.0 - Minimal disability in one FS (one FS grade 2, others 0 or 1).
- 2.5 - Minimal disability in two FS (two FS grade 2, others 0 or 1).
- 3.0 - Moderate disability in one FS (one FS grade 3, others 0 or 1) or mild disability in three or four FS (three or four FS grade 2, others 0 or 1) though fully ambulatory.
- 3.5 - Fully ambulatory but with moderate disability in one FS (one grade 3) and one or two FS grade 2; or two FS grade 3 (others 0 or 1) or five grade 2 (others 0 or 1).
- 4.0 - Fully ambulatory without aid, self-sufficient, up and about some 12 hours a day despite relatively severe disability consisting of one FS grade 4 (others 0 or 1), or combination of lesser grades exceeding limits of previous steps; able to walk without aid or rest some 500 meters.
- 4.5 - Fully ambulatory without aid, up and about much of the day, able to work a full day, may otherwise have some limitation of full activity or require minimal assistance; characterized by relatively severe disability usually consisting of one FS grade 4 (others 0 or 1) or combinations of lesser grades exceeding limits of previous steps; able to walk without aid or rest some 300 meters.
- 5.0 - Ambulatory without aid or rest for about 200 meters; disability severe enough to impair full daily activities (e.g., to work a full day without special provisions); (Usual FS equivalents are one grade 5 alone, others 0 or 1; or combinations of lesser grades usually exceeding specifications for step 4.0).
- 5.5 - Ambulatory without aid for about 100 meters; disability severe enough to preclude full daily activities; (Usual FS equivalents are one grade 5 alone, others 0 or 1; or combination of lesser grades usually exceeding those for step 4.0).
- 6.0 - Intermittent or unilateral constant assistance (cane, crutch, brace) required to walk about 100 meters with or without resting; (Usual FS equivalents are combinations with more than two FS grade 3+).

Appendix 4

Expanded Disability Status Scale (cont.)

- 6.5 - Constant bilateral assistance (canes, crutches, braces) required to walk about 20 meters without resting; (Usual FS equivalents are combinations with more than two FS grade 3+).
- 7.0 - Unable to walk beyond approximately 5 meters even with aid, essentially restricted to wheelchair; wheels self in standard wheelchair and transfers alone; up and about in wheelchair some 12 hours a day; (Usual FS equivalents are combinations with more than one FS grade 4+; very rarely pyramidal grade 5 alone).
- 7.5 - Unable to take more than a few steps; restricted to wheelchair; may need aid in transfer; wheels self but cannot carry on in standard wheelchair a full day; May require motorized wheelchair; (Usual FS equivalents are combinations with more than one FS grade 4+).
- 8.0 - Essentially restricted to bed or chair or perambulated in wheelchair, but may be out of bed itself much of the day; retains many self-care functions; generally has effective use of arms; (Usual FS equivalents are combinations, generally grade 4+ in several systems).
- 8.5 - Essentially restricted to bed much of day; has some effective use of arm(s); retains some self-care functions; (Usual FS equivalents are combinations, generally 4+ in several systems).
- 9.0 - Helpless bed patient; can communicate and eat; (Usual FS equivalents are combinations, mostly grade 4+).
- 9.5 - Totally helpless bed patient; unable to communicate effectively or eat/swallow; (Usual FS equivalents are combinations, almost all grade 4+).
- 10.0 - Death due to MS.

*Excludes cerebral function grade 1.

Note 1: EDSS steps 1.0 to 4.5 refer to patients who are fully ambulatory and the precise step number is defined by the Functional System score(s). EDSS steps 5.0 to 9.5 are defined by the impairment to ambulation and usual equivalents in Functional Systems scores are provided.

Note 2: EDSS should not change by 1.0 step unless there is a change in the same direction of at least one step in at least one FS.

Sources: Kurtzke JF. Rating neurologic impairment in multiple sclerosis: an expanded disability status scale (EDSS). *Neurology*. 1983 Nov;33(11):1444-52.

Source: [http://www.nationalmssociety.org/For-Professionals/Researchers/Resources-for-Researchers/Clinical-Study-Measures/Functional-Systems-Scores-\(FSS\)-and-Expanded-Disab](http://www.nationalmssociety.org/For-Professionals/Researchers/Resources-for-Researchers/Clinical-Study-Measures/Functional-Systems-Scores-(FSS)-and-Expanded-Disab)

Appendix 5
New York Heart Association Classification of
Functional Cardiac Capacity

Class	Description
I	No limitation: Ordinary physical activity does not cause undue fatigue, dyspnea, or palpitation.
II	Slight limitation of physical activity: Such patients are comfortable at rest. Ordinary physical activity results in fatigue, palpitations, dyspnea, or angina.
III	Marked limitation of physical activity: Although patients are comfortable at rest, less than ordinary physical activity will lead to symptoms.
IV	Inability to carry on physical activity without discomfort: Symptoms of congestive heart failure are present even at rest. With any physical activity, increased discomfort is experienced.

From: Criteria Committee, New York Heart Association, Inc. Diseases of the heart and blood vessels. Nomenclature and criteria for diagnosis. 6th ed. Boston, Little, Brown and Co, 1964:114.

Appendix 6

Guidance for Diagnosis of Progressive Multifocal Leukoencephalopathy

ACTION STEPS IF PROGRESSIVE MULTIFOCAL LEUKOENCEPHALOPATHY (PML) IS SUSPECTED:

- If the clinical presentation is suggestive of PML, further investigations should include brain magnetic resonance imaging (MRI) evaluation as soon as possible. If MRI evaluation reveals lesions suspicious for PML (see [Figure 1](#)), a lumbar puncture with evaluation of the cerebrospinal fluid (CSF) for the detection of JC virus (JCV) DNA should be undertaken. A diagnosis of PML can potentially be made by evaluating clinical and MRI findings plus the identification of JCV in the CSF.
- There is no known treatment or cure for PML. Treatment considerations are discussed in the medical literature (Calabrese et al. 2007).

MRI ASSESSMENT

- Although there are no pathognomonic findings that differentiate PML from MS, a brain MRI scan that includes fluid-attenuated inversion recovery (FLAIR) and T2-weighted and T1-weighted sequences, with and without gadolinium, should be performed to assess patients with neurological changes suggestive of PML (see [Figure 1](#)).
- Comparison with a baseline scan may assist with interpretation of the findings on the newly acquired MRI (see [Table 2](#) for differences in lesion characteristics that may help differentiate between PML and multiple sclerosis [MS]).

[figure not shown]
CSF ASSESSMENT

- The detection of JCV DNA in the CSF of a patient with clinical and MRI features suggestive of PML establishes the diagnosis of PML.
- If JCV DNA is not detected in CSF and if clinical suspicion of PML remains high, a repeat lumbar puncture should be performed.
- If diagnosis remains uncertain and suspicion of PML remains high, a brain biopsy may be considered to establish a definitive diagnosis.

Appendix 6
Guidance for Diagnosis of Progressive Multifocal Leukoencephalopathy (cont.)

Figure 1 Diagnostic Algorithm for PML

Suggested Diagnostic Algorithm

CSF=cerebrospinal fluid; JCV=JC virus; MRI=magnetic resonance imaging; MS=multiple sclerosis; PML=progressive multifocal leukoencephalopathy.

Appendix 6
Guidance for Diagnosis of Progressive Multifocal Leukoencephalopathy (cont.)

TABLE 1

Clinical Signs and Symptoms Typical of MS and PML*		
Onset	MS	PML
Acute	Subacute	
Evolution	
 ➤ Over hours to days ➤ Normally stabilized ➤ Resolve spontaneously even without therapy 	
 ➤ Over weeks ➤ Progressive
Clinical presentation	
 ➤ Diplopia ➤ Paresthesia ➤ Paraparesis ➤ Optic neuritis ➤ Myelopathy 	
 ➤ Cortical symptoms/signs ➤ Behavioral and neuropsychological alteration ➤ Retrochiasmal visual defects ➤ Hemiparesis ➤ Cerebellar symptoms/signs (e.g., gait abnormalities, limb incoordination)

Source: Kappos et al. 2007.

Appendix 6

Guidance for Diagnosis of Progressive Multifocal Leukoencephalopathy (cont.)

TABLE 2 MRI LESION CHARACTERISTICS TYPICAL OF PML AND MS

Feature	MS (relapse)	PML
Location of new lesions	Mostly focal; affect entire brain and spinal chord, in white and possibly gray matter	Diffuse lesions, mainly subcortical and rarely periventricular, located almost exclusively in white matter, although occasional extension to gray matter has been seen; posterior fossa frequently involved (cerebellum)
Borders	Sharp edges; mostly round or finger-like in shape (especially periventricular lesions), confluent with other lesions; U-fibers may be involved	Ill-defined edges; irregular in shape; confined to white matter; sparing gray matter; pushing against the cerebral cortex; U-fibers destroyed.
Mode of extension	Initially focal; lesions enlarge within days or weeks and later decrease in size within months	Lesions are diffuse and asymmetric, extending homogeneously; no confluence with other lesions; confined to white-matter tracks, sparing the cortex; continuous progression
Mass effect	Acute lesions show some mass effect	No mass effect even in large lesions (but lesion slightly abuts cerebral cortex)
On T2-weighted sequence	
 Acute lesions: hyperintense center, isointense ring, discrete hyperintensity outside the ring structure Subacute and chronic lesions: hyperintense with no ring structure 	Diffuse hyperintensity, slightly increased intensity of newly involved areas compared with old areas, little irregular signal intensity of lesions.
On T1-weighted sequence	Acute lesions: densely hypointense (large lesions) or isointense (small lesions); increasing signal intensity over time in 80%; decreasing signal intensity (axonal loss) in about 20%	Slightly hypointense at onset, with signal intensity decreasing over time and along the affected area; no reversion of signal intensity
On FLAIR sequence	Hyperintense, sharply delineated	Hyperintensity more obvious; true extension of abnormality more clearly visible than in T2-weighted images
With enhancement	
 Acute lesions: dense homogeneous enhancement, sharp edges Subacute lesions: ring enhancement Chronic lesions: no enhancement 	Usually no enhancement, even in large lesions; in patients with HIV, some peripheral enhancement is possible, especially under therapy.
Atrophy	Focal atrophy possible due to focal white-matter degeneration; no progression	No focal atrophy

Source: Yousry et al. 2006.

Appendix 7
2010 Revised McDonald Diagnostic Criteria for Multiple Sclerosis

Clinical (attacks)	Lesions	Additional Criteria to Make Diagnosis
2 or more	Objective clinical evidence of 2 or more lesions or objective clinical evidence of 1 lesion with reasonable historical evidence of a prior attack	None. Clinical evidence alone will suffice; additional evidence desirable but must be consistent with MS
2 or more	Objective clinical evidence of 1 lesion	Dissemination in space, demonstrated by 
 • ≥ 1 T2 lesion in at least two MS typical CNS regions (periventricular, juxtacortical, infratemporal, spinal cord); OR 
 • Await further clinical attack implicating a different CNS site
1	Objective clinical evidence of 2 or more lesions	Dissemination in time, demonstrated by 
 • Simultaneous asymptomatic contrast-enhancing and non-enhancing lesions at any time; OR 
 • A new T2 and/or contrast-enhancing lesions(s) on follow-up MRI, irrespective of its timing; OR 
 • Await a second clinical attack
1	Objective clinical evidence of 1 lesion	Dissemination in space, demonstrated by 
 • ≥ 1 T2 lesion in at least two MS typical CNS regions (periventricular, juxtacortical, infratemporal, spinal cord); OR 
 • Await further clinical attack implicating a different CNS site AND Dissemination in time, demonstrated by 
 • Simultaneous asymptomatic contrast-enhancing and non-enhancing lesions at any time; OR 
 • A new T2 and/or contrast-enhancing lesions(s) on follow-up MRI, irrespective of its timing; OR 
 • Await a second clinical attack

Appendix 7
2010 Revised McDonald Diagnostic Criteria for Multiple Sclerosis (cont.)

Clinical (attacks)	Lesions	Additional Criteria to Make Diagnosis
0 (progression from onset)		
One year of disease progression (retrospective or prospective) AND at least 2 out of 3 criteria:
 
 • Dissemination in space in the brain based on ≥ 1 T2 lesion in periventricular, juxtacortical or infratentorial regions; • Dissemination in space in the spinal cord based on ≥ 2 T2 lesions; 
OR
 
 • Positive CSF
2 or more	Objective clinical evidence of 2 or more lesions or objective clinical evidence of 1 lesion with reasonable historical evidence of a prior attack	None. Clinical evidence alone will suffice; additional evidence desirable but must be consistent with MS

CNS=central nervous system; CSF = cerebrospinal fluid; MRI=magnetic resonance imaging; MS=multiple sclerosis.

Sources:

http://www.nationalmssociety.org/NationalMSSociety/media/MSNNationalFiles/Brochures/Paper-TipSheet_-2010-Revisions-to-the-McDonald-Criteria-for-the-Diagnosis-of-MS.pdf

Polman et al. 2011.

Appendix 8

B-Cell Monitoring Schedule of Activities

	Prolonged B-Cell Monitoring^a
Assessment	Visits Every 24 Weeks (± 7 days)^b
Physical examination	x
Neurological examination	x
Vital signs	x
Routine safety laboratory tests^c	x
Urine pregnancy test	x
Hepatitis B virus DNA test^d	x
Total Ig, IgA, IgG, and IgM levels	x
Blood TBNK/B-cell subset panel^e	x
Recording of potential relapses	x
Adverse event assessments	x
Concomitant treatment review	x

HBcAb =hepatitis B core antibody; HBsAg =hepatitis B surface antigen; HBV =hepatitis B virus; PCR =polymerase chain reaction; TBNK =T cells, B cells, and natural killer cells.

^a Patients whose B-cells have not been repleted after 48 weeks of Safety Follow-up period will continue with visits every 24 weeks (± 7 days) until B-cell repletion (prolonged B-cell monitoring).

^b Visits will be performed at 24-week intervals counting from the date of last infusion of ocrelizumab.

^c Routine safety laboratory tests: hematology, chemistry, and urinalysis.

^d For enrolled patients with negative HBsAg and positive total HBcAb, HBV DNA (by PCR) must be repeated every 12 weeks.

^e Includes CD19 and other circulating B-cell subsets, T cells, natural killer cells, and other leukocytes.

1. BACKGROUND

Multiple sclerosis (MS) is a chronic, inflammatory, demyelinating, and degenerative disease of the central nervous system (CNS) that affects approximately 400,000 people in the United States (U.S.) and 2.5 million worldwide.

There remains an unmet medical need to develop more effective and well tolerated therapies for the treatment of MS. To meet this need, the identification of MS disease biomarkers represents a critical opportunity to potentially understand disease pathogenesis, disease progression, and the mechanism of action of a therapeutic treatment.

Ocrelizumab is a recombinant humanized anti-human monoclonal antibody that selectively targets CD20-expressing B cells. To better understand the mechanism of action of ocrelizumab in MS, this study will assess known biomarkers (OCBs, NfL, B cells, MRI as a surrogate marker, etc.) and explore new potential biomarkers associated with response to ocrelizumab in CSF and peripheral blood.

Refer to the protocol regarding more details of background on biomarkers in MS and background on Ocrelizumab.

2. STUDY DESIGN

This is an open-label, multicenter, biomarker study conducted at centers in multiple countries in which all eligible patients will be enrolled to a single treatment arm of ocrelizumab. The study will include an RMS cohort and a PPMS cohort. The RMS cohort is the main cohort and will include the majority of study participants. The RMS cohort will be comprised of four arms, three of which will have patients randomized into one of three arms (Arms 1-3) depending on the time of their second lumbar puncture (LP). In Arm 4, treatment with ocrelizumab will be delayed for 12 weeks after the first LP. The PPMS cohort will comprise a hypothesis-generating portion of the trial, as less is known about PPMS biomarkers.

The study treatment period is comprised of a Main Treatment Period and a Long-term Extension Period. For patients who complete the Main Treatment Period and continue to receive ocrelizumab, a Long-term Extension Period of the study will begin at Week 72 and administer ocrelizumab every 6 months for up to 4 years. The main treatment period will end on the earlier of the dates in which that patient received the Week 72 dose and the date in which Week 72 lab data were collected, or to data cutoff date or end of study date if patient hasn't received the week 72 dose. The long term extension period for each patient will start from the earliest day that patient takes the Week 72 dose or Week 72 lab data is collected till data cutoff date or end of study.

During the Main Treatment Period of the study, two LPs will be drawn from each patient. The two LPs will allow for assessment of biomarkers in CSF that are indicative of response to drug, pharmacokinetic/pharmacodynamic relationships, and/or disease pathogenesis in the CNS. Optional LPs may be collected upon patient's additional consent. Specifically:

Patients in the RMS cohort (Arms 1-3) will receive an LP before the start of dosing with ocrelizumab. Subsequently, these patients will be randomized into one of three arms for timing of the second LP, either Week 12, 24, or 52 following the first dose of ocrelizumab.

Patients in Arm 4 will receive two LPs, separated by a 12-week interval, before administration of the first dose of ocrelizumab. Patients in this arm will be asked if they are willing to give optional CSF samples via LP 12 weeks and 52 weeks after the ocrelizumab dose.

Patients in the PPMS cohort will receive an LP at the start of the study before dosing with ocrelizumab. Subsequently, they will receive a second LP at Week 52 following the first dose of ocrelizumab.

During the Long-term Extension Period, patients will be asked to consent to LPs performed every 2 years. Refer to the protocol regarding more details of study design including the long term extension period.

2.1 PROTOCOL SYNOPSIS

The Protocol Synopsis is in Appendix 1.

2.2 OUTCOME MEASURES

2.2.1 Primary Endpoints

The primary endpoints for the RMS cohort (Arms 1-3) include:

- Change in levels of NfL (pg/mL) in CSF from treatment baseline to post-treatment
- Change in number of CD19 + B cells in CSF (cell number/microliter) from treatment baseline to post-treatment
- Change in number of CD3+T cells in CSF (cell number/microliter) from treatment baseline to post-treatment

2.2.2 Exploratory Endpoints

The exploratory endpoints for RMS Arm 4 include:

Change from first LP to second LP comparing Arm 4 to Arm 1 in:

- Levels of NfL in CSF
- Number of CD19 + B cells in CSF

- Number of CD3 + T cells in CSF
- Levels of NfL in blood
- Number of CD19 + B cells in blood
- Number of CD3 + T cells in blood

The exploratory endpoints for the PPMS cohort are:

- Change in levels of NfL in CSF from treatment baseline to post-treatment
- Change in number of CD19 + B cells in CSF from treatment baseline to post-treatment
- Change in number of CD3+T cells in CSF from treatment baseline to post-treatment

For both RMS and PPMS cohorts, other exploratory endpoints include the impact of ocrelizumab treatment on other CSF biomarkers, blood biomarkers and MRI biomarkers listed in this section.

Change from treatment baseline in CSF biomarkers:

- %CD19+ B cell
- %CD3+ T cell
- %CD4+ (CD3+)
- CD4+CD3+ number
- %CD4- (CD3+)
- CD4-CD3+ number
- %IgD+CD27+ (CD19+)
- IgD+CD27+CD19+ number
- %IgD+CD27- (CD19+)
- IgD+CD27-CD19+ number
- %IgD-CD27- (CD19+)
- IgD-CD27-CD19+ number
- %IgD-CD27+ (CD19+)
- IgD-CD27+CD19+ number
- %CD138+CD38+ (IgD-CD27+)
- CD138+CD38+IgD-CD27+CD19+ number
- %CD138-CD38- (IgD-CD27+)
- CD138-CD38-IgD CD27+CD19+ number
- %CD138-CD38+ (IgD-CD27+)
- CD138-CD38+IgD-CD27+CD19+ number
- %CD38+ (IgD+CD27-)
- CD38+IgD+CD27-CD19+ number
- IgG
- IgM
- CXCL13
- CCL19
- Strem2

- YKL40
- IL-6

Change from treatment baseline in Blood biomarkers:

- %CD19+ B cell
- %CD3+ T cell
- CD3+ T cell number
- CD4+T cell number
- CD8+T cell number
- CD19+ B cell number
- CD56+CD16+ NK cell number
- CD4/CD8 Ratio
- NfL
- CXCL13
- IL-6

MRI biomarkers:

- Mean number of T1 Gd-enhanced lesions
- Mean number of new and/or enlarging T2 lesions
- Mean T2 lesion volume
- Mean Regional or total brain volume
- Mean number of leptomeningeal-enhancing regions

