Efficacy endpoints *for both cohorts* may include, but may not be limited to:

- Change in EDSS score from baseline

Other analyses may include evaluation of the possible associations between the changes in biomarkers of neurodegeneration or inflammation and change in MRI or efficacy outcome measures, such as reduction in Gd-positive lesions or *time to worsening as measured by the EDSS score (RMS and PPMS cohort), or the 25-foot timed walk or the 9-hole peg test (PPMS cohort only)*.

Endpoints for the RMS control arm (Arm 4) will include comparisons between Arm 1 of the RMS cohort (treatment baseline to second LP at 12 weeks) and Arm 4 (pre-treatment baseline to treatment baseline, second LP at 12 weeks before the first dose of study drug), and may include, but may not be limited to, changes in CSF at all collected timepoints including optional samples, blood, and MRI biomarkers or efficacy, as outlined above.

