- To assess potential correlation between change in blood or CSF biomarkers of neurodegeneration or inflammation and change in magnetic resonance imaging (MRI) or efficacy outcome measures, such as reduction in gadolinium (Gd)-positive lesions or Expanded Disability Status Scale (EDSS) score

The exploratory objectives for the Long-Term Extension are:

- *To understand the impact of ocrelizumab on indices of neurodegeneration*
- *To monitor the clinical condition of the patient over an extended period of time*

Exploratory objectives for the RMS delayed time to start control arm (Arm 4) will include comparisons between Arm 1 of the RMS cohort (second lumbar puncture [LP] at 12 weeks) and Arm 4 (*first* LP at 12 weeks before the first dose of study drug), and may include but not be limited to changes in CSF, blood, and MRI biomarkers or efficacy, as outlined above.

Pharmacokinetic Objective

The pharmacokinetic objective for this study is:

- To assess pharmacokinetics of ocrelizumab in CSF compared with serum concentration

Immunogenicity Objective

The immunogenicity objective for this study is:

- To assess the incidence of anti-drug antibodies to ocrelizumab

Safety Objectives

The safety objective for this study, *including for the Long-Term Extension*, is to evaluate the safety of ocrelizumab on the basis of the following endpoints:

- Nature, frequency, severity, and timing of adverse events
- Changes in vital signs, physical findings, and clinical laboratory results during and following ocrelizumab administration
- Adverse events related to biomarker sample collection

Study Design

Description of Study

This is an open-label, multicenter, biomarker study conducted at centers in multiple countries in which all eligible patients will be enrolled to a single treatment arm of ocrelizumab. The study will include an RMS cohort and a PPMS cohort (see Table 1). The RMS cohort is the main cohort and will include the majority of study participants. The RMS cohort will be comprised of four arms, three of which will have patients randomized into one of three arms (Arms 1–3) depending on the time of their second LP. In Arm 4, treatment with ocrelizumab will be delayed for 12 weeks after the first LP. The PPMS cohort will comprise a smaller, hypothesis-generating portion of the trial, as less is known about PPMS biomarkers.

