Patients who complete the study and choose not to continue on ocrelizumab treatment, or who discontinue from treatment early, should enter the Safety Follow-up Period and be assessed every 24 weeks for 48 weeks counting from the date of the last infusion of ocrelizumab. After 48 weeks, if the peripheral blood B-cell count remains depleted, monitoring of the patient should continue at 24-week intervals until the B-cell count has returned to the baseline value or to the lower limit of the normal range, whichever is lower (see Appendix 8).

For patients who complete the study and continue to receive ocrelizumab, a Long-Term Extension of the study beginning at Week 72 will be conducted every 6 months for up to 4 years at the time of treatment infusion for as long as they continue to receive ocrelizumab (Appendix 9). A Long-Term Extension of the study is needed to understand the correlation between long-term changes in biomarker assessments with long-term safety and long-term efficacy of ocrelizumab. The Long-Term Extension extends the study to a total of 5 years, which is the necessary timeframe to investigate whether baseline CSF NfL levels may be prognostic for long-term brain atrophy as assessed by 5-year declines in whole brain volume in MS patients (Arrambide et al. 2016). CSF NfL and serum NfL levels are highly correlated in the disease (Disanto et al. 2017), and therefore measurement of blood NfL levels may allow for predictions of brain atrophy in MS patients. Treatment of MS patients with disease-modifying therapies has been demonstrated to cause short-term (6 months to 1 year) accelerations in whole brain-volume loss (pseudoatrophy) but slows long-term (3 – 5 years) brain atrophy (Zivadinov et al. 2008). Therefore, a Long-Term Extension is needed in order to accurately establish an association between serum NfL levels and brain atrophy in patients in the study.

Biomarkers will be monitored in a longitudinal fashion before and after treatment with ocrelizumab in order to assess dynamic changes in biomarkers as they relate to drug exposure, length of time on drug, response to drug, and MS disease pathogenesis. Biomarkers will be assessed via blood draws throughout the study and via LP in CSF at baseline before the first dose of ocrelizumab and at one other timepoint.

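### The SAP names no disability outcome as an endpoint or association, although its own synopsis keeps the aim of relating biomarker change to EDSS; any such result would be post hoc

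*SAP*

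**What the plan says.** **Objectives.** The protocol synopsis in SAP Appendix 1 aims to correlate change in blood or CSF biomarkers with change in MRI or "efficacy outcome measures, such as reduction in gadolinium (Gd)-positive lesions or Expanded Disability Status Scale (EDSS) score". For the long-term extension (LTE) it adds "To monitor the clinical condition of the patient over an extended period of time", and it justifies the LTE by the need to "understand the correlation between long-term changes in biomarker assessments with long-term safety and long-term efficacy of ocrelizumab".

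**Protocol endpoints.** Protocol 6.4.2 gives "Change in EDSS score from baseline" as an efficacy endpoint for both cohorts. It also lists possible associations of biomarker change with "time to worsening as measured by the EDSS score (RMS and PPMS cohort), or the 25-foot timed walk or the 9-hole peg test" (the timed tests in PPMS only). Both items are worded permissively, as things that may be included.

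**SAP endpoints and analyses.** SAP 2.2.2 says that, for both cohorts, "other exploratory endpoints include the impact of ocrelizumab treatment on other CSF biomarkers, blood biomarkers and MRI biomarkers listed in this section". The lists that follow contain CSF, blood and MRI measures only. SAP 4.4.2.3 names seven Spearman associations and four Mann-Whitney comparisons. None involves EDSS, the 25-foot walk or the 9-hole peg test.

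**The concern.** An objective restated in the SAP has no named disability endpoint, pairing or visit behind it. The choices left open are the change measure, the visit, the biomarker, whether to pool arms, and what counts as worsening. Neither document gives an EDSS worsening threshold or confirmation rule apart from the relapse definition. For the timed tests, Protocol 4.5.6 gives a 20% change, but the SAP does not take it up.

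The study is open-label. SAP 2.4 and 4.8 describe several interim analyses performed and interpreted by the sponsor's team, and the first has already been conducted. If the EDSS definition and pairing are chosen after data have been seen, a reader cannot tell a planned correlation from a selected one. The gap is widest in PPMS: two timed tests are collected in that cohort specifically, and the SAP makes no use of them.

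**Working it through.** **1. Objective against plan.**

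| Measure | Collected (protocol schedules) | Named in SAP endpoints or associations | Elsewhere in SAP |
|---|---|---|---|
| EDSS | Arms 1–3 and PPMS: Week 1 plus Weeks 12, 24, 36, 48, 52. Arm 4 also Week -12 | No | Baseline characteristic (4.3.2); window table to Week 240 (Appendix 2) |
| 25-foot walk, 9-hole peg | PPMS: Week 1 plus Weeks 12, 24, 36, 48, 52 | No | Not mentioned |
| Relapse | All arms | Yes: CSF NfL percent change by relapse status (4.4.2.3); primary endpoints by relapse status (4.4.4) | Summary in safety population (4.6) |
| MRI | All arms | Yes: T1 Gd lesions, new/enlarging T2 lesions, brain volume | Endpoints in 2.2.2 |

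SAP 4.4.1, 4.4.3 and Table 2 add no disability outcome.

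**2. Can the existing EDSS windows support a Week 52 analysis?** In the EDSS table of Appendix 2, Week 36 covers days 211–294, Week 48 covers 295–350, and Week 52 starts at day 267.
- Overlap with Week 36: days 267–294, which is 294 − 267 + 1 = 28 days.
- Overlap with Week 48: days 295–350, which is the whole window, 350 − 295 + 1 = 56 days.

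An assessment on nominal day 336 therefore belongs to both Week 48 and Week 52. Day 267 is also the Week 52 start in the MRI and CSF tables, which have no Week 36 or 48 visit. The blood biomarker table, which has both visits, starts Week 52 at day 351.

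**3. What could such correlations detect?** The plan's only sample-size calculation is for CSF NfL change. It reproduces: SD of change = √(780² + 310² − 2 × 0.6 × 780 × 310) = 643.7, and a paired t-test of 860 − 602 = 258 pg/mL has power 0.802 at n = 51. Nothing is sized for EDSS.

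For a Spearman correlation at two-sided 5% and 80% power, I assume the Fisher z approximation with variance 1.06/(n − 3):

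|ρ| = tanh[(1.960 + 0.842) × √(1.06/(n − 3))]

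The n values are the evaluable numbers in SAP 2.3: Arm 1 15, Arm 2 25, Arm 3 26, PPMS at least 15.

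| Analysis | n | Detectable absolute ρ |
|---|---|---|
| Blood biomarkers, Arms 1–3 pooled (15 + 25 + 26) | 66 | tanh(2.802 × 0.1297) = 0.35 |
| CSF at Week 52, Arm 3 | 26 | tanh(2.802 × 0.2147) = 0.54 |
| CSF at Week 24, Arm 2 | 25 | 0.55 |
| CSF at Week 12, Arm 1; PPMS at its minimum | 15 | 0.68 |

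If all of the approximately 30 PPMS patients mentioned in SAP 2.3 were evaluable, the PPMS value would be about 0.50.

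The pooled figure does not carry over to Week 52 CSF. Among Arms 1–3 only Arm 3 has a scheduled lumbar puncture then. In Arms 1 and 2 the Week 52 puncture is optional, and extension punctures depend on further consent. The approximation also ignores ties, which EDSS change in half-point steps will produce.

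**The case against.** The other side has a good case on several points.

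- **The data exist.** EDSS is collected and windowed to Week 240, and SAP 4 and 4.4.2.3 allow Spearman correlation with unspecified clinical parameters. A reader might infer that the EDSS aim cannot be answered. The documents do not support that: the analysis is possible but not pre-specified.
- **Clinical outcomes are not confined to safety.** A reader might infer that relapse in the safety section is the only clinical outcome. It is not: the efficacy section compares CSF NfL change by relapse status and summarises all three primary endpoints by relapse status. What is missing is disability.
- **The aims are partly served.** The synopsis objective is met by MRI or efficacy measures, and changes in CSF NfL, CD19+ and CD3+ cells are paired with change in Gd lesions. The LTE rationale goes on to brain atrophy, and CSF NfL with brain volume is listed. Blood NfL with brain volume, which that rationale also raises, is not.
- **The protocol items are optional.** Omitting them breaks no commitment. But the objectives are not worded as optional, and the SAP is where options are settled.
- **Some sources are unavailable.** SAP 4.9 defers the output list to Module 2. The SAP's synopsis is from protocol Version 5 (U.S.), while the 6.4.2 text is Version 4 (Global), and the LTE schedule was not available. The Version 5 synopsis retains the EDSS objective but does not mention the timed tests. An output list could contain EDSS tables, but it would not replace an endpoint definition.

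**Conclusion.** The point holds as a pre-specification gap. The SAP restates an objective of relating biomarker change to EDSS, adds one on long-term clinical condition, and names no disability endpoint or association for either. Any disability result would be post hoc. Relapse and MRI analyses partly fill the gap.

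Its size is modest. The study is mostly descriptive, and disability correlations would be unpowered: about 0.35 detectable in pooled blood analyses and 0.54 or larger in single-arm CSF analyses, on the approximation and evaluable numbers above. It is worth fixing because main-period EDSS and timed-test data are already scheduled. The conclusion assumes that Module 2 and the Version 5 protocol body contain no definition that the SAP text lacks.

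**What to change.** 1. In SAP 2.2.2, add change from treatment baseline in EDSS (both cohorts) and in 25-foot walk and 9-hole peg time (PPMS, main period; LTE only if collected).
2. In SAP 4.4.2.3, add descriptive Spearman correlations of:
   - (a) change in blood NfL, CD19+ and CD3+ with change in EDSS at Week 52 and, where available, Week 240, with Arms 1–3 pooled and PPMS separate;
   - (b) change in CSF NfL, CD19+ and CD3+ at each arm's second lumbar puncture with change in EDSS at the same visit, by arm, with PPMS at Week 52;
   - (c) the same biomarkers with change in the two timed tests in PPMS.
3. Either define time to worsening (measure, threshold, any confirmation rule, method) or state that it is not analysed.
4. In Appendix 2, add windows for the timed tests and correct the EDSS Week 52 window so that it no longer overlaps Weeks 36 and 48. Starting it at day 351 would match the blood biomarker table.
5. State that these analyses are unpowered, with the detectable correlations above.

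The cost is SAP text, some window programming and a few more descriptive, unpowered tables. The main-period analyses need no extra assessments.
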